## **6.6 Measures**

**General Questionnaire.** This questionnaire will include basic demographic and health questions that will be self-reported by the subjects. This may include questions about their medical history, psychiatric history, substance use history, and current medications. Since our study requires a return visit, this questionnaire may also include participant contact information.

**Behavioral.** The following tests may be included in the online surveys:

*Pittsburg Sleep Quality Index (PSQI):* This 19-item scale yields component scores for seven different domains of sleep quality: subjective sleep quality, sleep latency, sleep duration, habitual sleep efficiency, sleep disturbances, use of sleep medication, and daytime dysfunction. We will use this measure to assess for changes in self-reported sleep quality across the study period. This measure may be administered at intake, week 2, week 4, and follow-up.

*Epworth Sleepiness Scale (ESS):* This 8-item questionnaire assesses daytime sleepiness by having participants rate their usual chances of dozing off while engaged in common activities. We will use this measure to assess for changes in self-reported daytime sleepiness across the study period. This measure may be administered at intake, week 2, week 4, and follow-up.

*Patient Health Questionnaire-8 (PHQ-8):* This 8-item questionnaire assesses depressive symptoms, and we will use it as a mental health outcome measure. We will adjust the time scale to asking about symptoms over the past week. This measure may be administered at intake, week 2, week 4, and follow-up.

*Generalized Anxiety Disorder-7 (GAD-7):* This 7-item questionnaire screens for symptoms of generalized anxiety disorder and characterizes their severity, and we will use it as a mental health outcome measure. We will adjust the time scale to asking about symptoms over the past week. This measure may be administered at intake, week 2, week 4, and follow-up.

*Perceived Stress Scale (PSS):* This 10-item questionnaire measures the degree to which situations in one's life are appraised as stressful. In particular, it gauges how unpredictable, uncontrollable, and overloaded respondents find their lives. We will adjust the time scale to asking about symptoms over the past week and use this measure to track potential changes in stress levels. This measure may be administered at intake, weekly, and at follow-up.

*Positive and Negative Affect Schedule (PANAS):* *Positive emotions* (overall, serenity, joviality, self-assurance) and *negative emotions* (overall, sadness, fear, hostility) will be

measured with 17 adjectives each. This measure will be used to assess changes in self-reported emotions. This measure may be administered at intake, weekly, and at follow-up.

*Multidimensional Assessment of Interoceptive Awareness-2 (MAIA-2).* Interoceptive awareness will be assessed as a potential proximal outcome of mindfulness practice. We will use the body listening (3 items), trusting (3 items), and self-regulation (4 items) subscales (10 items total). These subscales may be administered at intake, weekly, and at follow-up.

*Applied Mindfulness Process Scale (AMPS).* The AMPS scale measures mindful emotion regulation – decentering, positive emotion regulation, and negative emotion regulation. This measure will be used to assess for changes in mindful emotion regulation associated with longitudinal use of the mindfulness app. The 15-item scale may be administered at intake, week 2, week 4, and follow-up.

The Nondual Awareness Dimensional Assessment - State (NADA-S). This 3-item scale measures mindfulness-related processes of self-transcendence. We use it to assess changes in self-transcendence associated with the use of the mindfulness app. The scale is administered at intake, weekly, and at follow-up.

*PERMA Profiler.* This questionnaire measures flourishing across 5 domains: positive emotion, engagement, relationships, meaning, and accomplishment following [name] well-being theory. We will use this 19-item measure to assess for changes in self-reported well-being. This measure may be administered at intake, week 4, and at follow-up.

*Pain Numeric Rating Scale:* Participants will be asked to rate their current pain level on a scale from 0-10 (0 = no pain at all, 10 = highest level of pain imaginable), as tVNS and mindfulness may provide pain relief. This measure may be administered at intake, weekly, and at follow-up.

*System Usability Survey (SUS).* This is a standard version of a usability scale. Participants will be given 10 statements regarding the usability of the equipment they used, and they will report how much they agree with each statement on a 1 – 5 scale. This measure will only be given after the completion of the intervention phase (week 4).

*Acceptability of Intervention Measure (AIM), Intervention Appropriateness Measure (IAM), and Feasibility of Intervention Measure (FIM).* These brief 4-item scales measures the degree to which participants believe an intervention is acceptable, appropriate, and feasible. These measures will only be given after the completion of the intervention phase (week 4).

**Physiological.** Subjects will be given a Fitbit brand wristband that offers real-time physiological data acquisition to use to monitor their sleep quantity, quality, and overnight heart rate variability (HRV) during the intervention phase. Participants will also be given a Polar H10 chest strap to use during mindfulness sessions, measuring their momentary HRV. Participants may be provided a preassigned account and password for these wearable devices, which may be accessed by the research team to manage raw data.

#### **Analysis Plan.**

- To analyze feasibility data, we will qualitatively examine rates of recruitment and drop out/attrition and compare them to prior research. Quantitatively, to examine whether dropout is selective, participants who completed the study will be compared to participants who dropped out on group via chi-square independence test. To analyze acceptability data, outcomes regarding tolerance and acceptability will be compared between the groups via

ANOVA. In addition, we will perform thematic analysis of participant responses to open-ended questions about feasibility and acceptability.

- To examine trajectory of sleep and mental health/well-being over time, multilevel modeling (MLM) analyses will be conducted using unrestricted full information maximum likelihood in R via the “lme4” package. Separate models will be conducted using each sleep and mental health/well-being outcome measure as a dependent variable. Linear and quadratic time trends will be estimated, and intervention group will be included as a moderator. To examine adherence, the number of minutes participants spend engaged with the app or tVNS device per week will be averaged. Then, an MLM will be conducted using average weekly engagement as the dependent variable and time (linear and quadratic) and group as predictors. Retention rates between intervention groups will be compared using an independent samples t-test.

**Nerve Stimulation.** The auricular branch of the vagus nerve projects to the brainstem and is accessible via electrical stimulation through surface electrodes. Stimulation produces vagus sensory evoked potentials not induced with off-target stimulation.

**Earpiece Placement:** All subjects will be instructed to place the Soterix device earpiece on their left ear such that the stimulation electrode is positioned over the inner tragus and the return electrode is positioned just anterior to the tragus to minimize off-target stimulation per local pilot protocol (see Figure 2). Subjects will demonstrate their ability to set up the stimulator—including earpiece placement—and text the picture of the electrode placement with their faces occluded, similar to Figure 2. Research assistants will also provide a link with an instructional video that participants can refer to in order to ensure they have properly placed their electrodes. Participants will be asked to send a photo of their electrode placement for each stimulation session via SMS.

**Stimulation Device:** We will use the Soterix Medical RELIfit-Tragus transcutaneous electrical nerve stimulation devices. For details, see “Device type” in my.irb. Stimulus pulses will be alternating in polarity to reduce tissue irritation and will be delivered at 20Hz, 200  $\mu$ s pulse width, within the range of published stimulus parameters.

**Calibration:** Participants will undergo calibration during the intake-training visit. Prior to calibration, participants will be informed that the stimulation intensity will be slowly increased until they report any discomfort and then reduced to a comfortable level for the remainder of the study. Individual sensitivity to tVNS stimulation will then be evaluated with a structured stepped-ramp protocol, with a brief pause at each step during which the participant will be asked what the stimulus felt like to them and if they experienced any discomfort. The stimulation intensity will then be set to 80% of the discomfort threshold for the active tVNS group and near to 0% (just enough to keep device on) of the discomfort threshold for the sham stimulation group. If the participant reports irritation with stimulation during this ramp up procedure (which can last ~15 minutes), electrode adhesion will be checked (if there is poor contact, it can affect the sensation) and stimulation intensity will be reduced if necessary (any change will be documented). If the participant further indicates discomfort, stimulation will be discontinued. If the patient evidence dizziness/lightheadedness or if a comfortable level of stimulation is not achievable at calibration, the participant will be removed from the study (this will be documented).

**Blinding:** Participants will be blinded to condition and told that, after calibration, the stimulus intensity will be set to below the calibration (discomfort threshold) level and that they may not feel the stimulation once reduced. We have used this form of psychological sham approach in

the past. Participants will be provided with a maximum of 14 blinding codes that correspond with the appropriate stimulation parameters and intensity depending on their group assignment. These blinding codes must be entered into the tVNS device in order for stimulation to be administered. They are one-time use only, meaning that participants will not be able to administer tVNS more frequently than instructed in the study protocol. Moreover, participants will be told that these blinding codes correspond to stimulation parameters/intensity that is calibrated to them only, and that they are not safe to be used on other people (e.g., friends, roommates). The picture of earpiece placement that participants send with each stimulation session should act as a further control against participants allowing others to use the stimulation device. The blinding codes will also specify stimulation length, with a maximum of one hour (after which, stimulation will be turned off). Of note, stimulation also turns off if there is not good connectivity between the earpiece and the tragus (e.g., if the earpiece falls off or if it is placed on another part of the body without adequate connectivity).

*At-Home Device Use:* Per the Soterix website: “The Soterix Medical taVNS device is intended for use by, or under the direct or remote supervision of, a trained healthcare practitioner.” We have discussed this statement via email with [name], CEO and CTO of Soterix Medical, who clarified that “By trained health care practitioner- we simply mean someone who is aware of taVNS, technology, risks, etc. and knows how to administer the technique”, and “By remote supervision- the system can be self-administered. The subject or caregiver (proxy in some cases) would need to be trained on placing the electrodes before they become eligible. The system is designed such that the administrator (PI, clinical center personnel,etc) sets the desired dose (duration, frequency, pulse width, etc) before handing it off to the subject. The subject can only deliver stimulation as prescribed by the clinic [or lab] (i.e. cannot misuse). So basically a researcher can remotely supervise administration.” This email correspondence is attached as supplementary material. Given this clarification, our study protocol (e.g., with staff training participants on electrode placement/device use and subsequent at-home self-administration with “remote supervision”) is consistent with Soterix Medical’s intended use of the device. We will be receiving pictures of electrode placement for each stimulation session.

*Investigational Device Exemption (IDE):* An Investigational Device Exemption is not necessary per communication with the FDA and rules governing assessment of risk if the study is a non-significant risk (NSR) investigation.

**Figure 2** Non-invasive vagal nerve stimulation earpiece placement.

**Mindfulness Mobile App:** The Brightmind mindfulness training app provides lessons by leading American mindfulness teacher and neuroscience research consultant Shinzen Young. His exercises have been shown to be effective in reducing physiological stress reactivity and improving positive affect in previous randomized experimental studies among community adults in the Pittsburgh area. A full description of the lessons is attached as supplemental material. Participants in our study will be instructed to start with the “Stress Less” introductory course of 8 sessions. Every session includes a brief explanation of how the practice helps reduce stress.

- Session 1, Get Grounded – focus on hearing sound or silence, physical body sensations, focus on what you see, acknowledge emotional state, let stressful thoughts and feelings come and go in the background with relaxed body and slight smile
- Session 2, Relaxation – enjoy rest and relaxation, notice what relaxation feels like by tensing and loosening muscles in every part of body, then whole body
- Session 3, Training Positivity – come up with word or phrase that helps overcome stress, mentally repeat; find a positive, relaxing mental image, hold it; create positive emotional sensation in body that relates to positive phrase and image
- Session 4, Untangle and Be Free – notice mental images or blank screen, notice mental talk or silence, notice emotional sensations in body or rest – develop flexibility, observer mindset
- Session 5, Soothing Sound – noting technique – acknowledging and focusing on sensory experience - sounds or silence, every few seconds
- Session 6, Focused Relaxation – noting relaxation in body every few seconds, tightening & loosening of muscles
- Session 7, Anchoring Awareness in the Body – noting physical sensations, labeling technique – name sensory experience, “feel”
- Session 8, You’re Not (Just) Your Thoughts – noting mental talk or silence every few seconds, observer mindset, labeling technique – name mental talk “hear”, absence of mental talk “rest”

After finishing the introductory course, participants will gain access to suggested next courses, “Mindful Awareness” (7 sessions) and “Deepen Your Practice” (8 sessions).

Participants will be provided a pre-assigned account and password to use with this app, which will be accessed by the research team to manage raw data collected through the app (e.g., session type, number of sessions, and time spent in the app). The use of pre-assigned accounts and passwords will make it such that any data collected by the app will be de-identified.

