The current study explores using tVNS as a potential method to alleviate barriers to establishing a habit of mindfulness practice. In mindfulness interventions it is not uncommon for participants to report an initial escalation of anxiety and distress as they directly engage with negative thoughts. While accepting, decentering, and deriving meaning from these negative reactions is an important feature of the psychotherapeutic process in mindfulness interventions, they can also lead to disengagement or drop out from the intervention. Similarly, difficulty learning the skill of meditation is also common and can contribute to participant dropout. tVNS may exert an anxiolytic effect through effects on limbic structures and activation of the parasympathetic nervous system. Moreover, tVNS increases positive affect (i.e. calm) and has been linked to improved interoceptive awareness, which are two other potential psychological mediators of mindfulness interventions. Thus, these two separate treatment approaches appear complementary, yet there are no published trials using them in combination. **The proposed study will enable us to evaluate the utility of this combined treatment approach in enhancing college student sleep and mental health, with potentially broader impacts for clinical populations.**

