Control (n = 20)	
 
- Engage with the control task for 10 minutes each evening for 4 weeks
 
- Wear the Polar H10 chest strap during the control task at least 1x/week
 
- Wear the Fitbit overnight for 4 weeks
 

**Table 1.** Intervention phase procedures for each experimental group.

**6.3 Subjects.** This study utilizes a between-participant design and will recruit 80 healthy college students aged 18 – 30. Pregnant women may not participate in this study—pregnancy tests provided by the study will be used for women of child-bearing age randomized to a tVNS group prior to starting the study and after the consenting process. Pregnancy tests will only be given in the intake session.

**6.4 Recruitment and Retention.** We will recruit a volunteer sample of undergraduate students from the Gainesville, Florida community who are interested in managing stress. We will post IRB-approved flyers around the community and on the UF campus. The flyers include a survey link where interested students can provide their contact information if they believe they qualify for the study to allow study staff to contact them to schedule an intake appointment. The investigators will be involved in recruitment of participants from multiple sources, including campus tabling events, posting flyers on UF campus and through GatorWell, emails to relevant listservs, making announcements during undergraduate classes, and through word of mouth. The investigators will also post announcements to Facebook and Twitter (see Social Media Strategy). Subjects will be expected to provide their own means of transportation.

**6.5 Inclusion/Exclusion Criteria.** Participants will include adults between the ages of 18-30, consistent with the typical college population. Participants must own a smartphone, be able to read and write English, and not be in ongoing psychotherapy.

Major medical illnesses including diagnosed severe neurological illnesses (e.g., stroke, seizure history), medical conditions associated with neurological effects (e.g. heart, kidney disease), autoimmune disorders, and severe psychiatric diseases (e.g., schizophrenia) will be excluded. Participants with any history of brain surgery, tumor, intracranial metal implantation, pacemakers or other implanted devices will be excluded. These elements will be assessed via self-report.

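### Selective dropout is tested only by arm, so dropout related to intake or early on-study distress but balanced across arms would go undetected

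*Combined protocol and SAP*

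**What the plan says.** The Analysis Plan in section 6.6 gives the purpose, "Quantitatively, to examine whether dropout is selective", and then the method: "participants who completed the study will be compared to participants who dropped out on group via chi-square independence test". Arm is the only variable named. The other quantitative attrition analysis is also by arm: "Retention rates between intervention groups will be compared using an independent samples t-test". Recruitment and attrition rates are otherwise examined qualitatively against earlier research, and open-ended answers are analysed by theme.

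The Abstract (section 3) explains why participants might leave. It is not unusual for "participants to report an initial escalation of anxiety and distress as they directly engage with negative thoughts", and of these reactions it says that "they can also lead to disengagement or drop out from the intervention". It adds that "difficulty learning the skill of meditation is also common and can contribute to participant dropout". It also expects stimulation to ease the problem: "tVNS may exert an anxiolytic effect through effects on limbic structures and activation of the parasympathetic nervous system".

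Section 6.2 has every participant complete mood and sleep measures at intake. Section 6.6 lists the PSQI, PHQ-8, GAD-7 and PSS at intake, and the PSS and PANAS weekly as well, all as measures that may be given. Each outcome has its own multilevel model, fitted by full information maximum likelihood. No missing-data assumption or sensitivity analysis is stated.

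**The concern.** Selectivity is about which participants leave. A test on arm answers a narrower question, whether attrition differs between arms. The two come apart when distress raises the chance of leaving by the same amount in every arm: the participants who remain are a selected group, yet the arm rates agree.

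This matters because Aims 1 and 3 in section 5 concern feasibility and acceptability, so who leaves is part of the result. A null chi-square could easily be read as showing that dropout was not selective, although the test had no means of finding this kind of selection. The intake data that could show it are collected, but no section plans to use them for this.

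**Working it through.** **Stated figures.** The documents give no dropout rate, alpha or power for this test, so there is no figure to reproduce.

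**Inputs.** From the documents: section 6.3 "will recruit 80 healthy college students aged 18 – 30", and Table 1 gives four arms of 20, three with mindfulness and one control. Assumed: two-sided alpha 0.05; dropout of 10%, 20% or 30%; odds ratios of 1.5, 2 and 3 per SD of intake distress; the same distress distribution in each arm.

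**Why the planned test cannot see balanced selection.** Let z be the standardised intake score and let P(dropout | z) = 1/(1 + exp(−(a + bz))) in every arm. Averaging over z gives the same dropout probability in each arm for any b. The chi-square null hypothesis (4 × 2 table, 3 degrees of freedom) is then true whatever the value of b, so its rejection rate stays near alpha.

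**Simulation.** At least 3,000 trials per setting. Planned test: Pearson chi-square of arm by dropout. Added comparison: two-sample t-test of z, dropouts against completers. The chi-square rejected in 3.7% to 5.6% of trials across these settings. The added comparison rejected as follows:

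| Dropout | OR 1.5 | OR 2 | OR 3 |
|---|---|---|---|
| 10% | 17% | 41% | 75% |
| 20% | 30% | 65% | 94% |
| about 30% | 35% | 76% | 98% |

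In the last row the OR 1.5 and OR 3 cells had realised dropout of 30.5% and 33.5%. Repeat runs differed by up to about four points.

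**Distress acting only in the mindfulness arms** (OR 2 to 3, underlying dropout 20% to 30%): chi-square about 6%, intake comparison 43% to 84%.

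**Dropout caused by practice itself**, with control at 10% and no link to intake score:

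| Mindfulness arms | Chi-square rejects |
|---|---|
| 20% | 10% |
| 30% | 29% |
| 40% | 58% |
| 50% | 84% |

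Here the intake comparison rejects only about 5% of the time, so it cannot replace the arm comparison.

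**Opposite directions.** With OR 2 in two arms and 0.5 in the other two, the chi-square rejects about 4% and a pooled intake comparison about 6%. Only arm-specific estimates or an interaction can show this pattern.

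**Precision.** At 20% dropout there are 80 × 0.20 = 16 dropouts and 64 completers. The 95% half-width for a mean difference is 1.99 × √(1/16 + 1/64) = 1.99 × 0.280 = 0.56 SD. At 10% (8 against 72) it is 1.99 × √(1/8 + 1/72) = 0.74 SD. Within one arm (4 against 16) it is 2.10 × √(1/4 + 1/16) = 1.17 SD.

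**The case against.** The strongest reply is that arm is the relevant variable. A reader might infer that intake distress is the dropout mechanism the protocol itself describes. It is not: the Abstract describes distress that rises during practice, and difficulty with the skill. Three arms practise and one plays a number puzzle, and stimulation is expected to reduce anxiety. That mechanism can therefore produce a difference between arms, and the chi-square has some power against it. This stands. It is a reason to keep the arm comparison, and it rules out the claim that distress-driven dropout would always be declared non-selective. The documents also contain no rule for making such a declaration.

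A second reply is that likelihood models tolerate dropout that depends on scores they contain. This largely stands. In a two-wave check with OR 3 and 21% dropout, a true arm difference of 0.50 was recovered as 0.49. A reader might infer that the planned outcome estimates are biased, or that comparing intake scores would test missing at random. Neither follows: that assumption concerns unobserved values. What remains is narrower. Each outcome is modelled alone, so dropout that depends on anxiety is not accounted for in a PSQI model unless anxiety is added. The size of that effect was not calculated.

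A third reply is that extra tests create false flags. Four independent tests at 0.05 flag at least one scale in 1 − 0.95⁴ = 18.5% of trials with no selection; with an assumed correlation of 0.5, simulation gave about 15%. Choosing covariates from those flags would be post hoc. This stands, and it shapes the fix.

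**Conclusion.** The concern holds in limited form. The selectivity check uses arm alone, so it cannot detect dropout related to distress that is balanced across arms. Its rejection rate stays at about 4% to 6%, against about 41%, 65% and 76% for an intake comparison at 10%, 20% and 30% dropout with an odds ratio of 2 per SD. The rates for the intake comparison rest on an assumed alpha, dropout rate and odds ratio. The blindness of the chi-square rests only on selection being equal across arms and on similar intake distress in each arm. The same reasoning covers early on-study distress if it is balanced across arms, though only an intake score was simulated.

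The main consequence is for the feasibility conclusion. The documents do not show that the efficacy estimates are biased.

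**What to change.** 1. Keep the arm comparison, but report the dropout proportion in each arm with an exact confidence interval. For example, 4 of 20 is 20%, with exact 95% limits of 5.7% and 43.7% (the 2.5% point of Beta(4, 17) and the 97.5% point of Beta(5, 16)).
2. Compare dropouts with completers on intake PSQI, PHQ-8, GAD-7 and PSS, and on the last observed weekly PSS and PANAS. Do this overall and by arm, with arm-specific estimates or an arm interaction. Report estimates with confidence intervals, not pass/fail tests.
3. Add a sensitivity multilevel model for each outcome, with a small set of intake distress scores named in advance as auxiliary covariates. Leave out the outcome's own intake score where it is already a row in the model. Do not select covariates by dropout p-values.
4. Word the result as a description of who left, with no claim that missing at random has been verified.

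The cost is a few table rows and one extra model per outcome, on data already scheduled. The drawback is imprecision: with few dropouts, and above all within arms, the intervals will be wide.
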